## ABSTRACT

### Background

Evidence suggest that the mesentery is involved in patients with Crohn's disease (CD). Data on the anti- or pro-inflammatory role of the mesentery are conflicting. It is suggested that extended mesenteric resection – removing an increased volume of mesentery – might result in decreased postoperative recurrence rates in patients undergoing ileocolic resection (ICR). The SPICY study was designed to analyse whether extended mesenterectomy is superior to mesenteric sparing ICR. This manuscript presents the statistical analysis plan (SAP) to evaluate the outcomes of the SPICY trial.

**Design and methods:** The trial was designed as an international randomised controlled superiority trial, allocating patients (1:1 ratio) to either group 1—mesenteric sparing ICR or group 2—extended mesenteric ICR, up to the level of the ileocolic trunk. To detect a clinically relevant difference of 25 per cent in endoscopic recurrence at 6 months, a total of 138 patients were required (including 10 per cent dropout). Patients aged  $\geq 16$  years with CD undergoing primary ICR were counselled for inclusion. Primary outcome is the 6-month postoperative endoscopic recurrence rate (modified Rutgeerts score  $\geq 2b$ ), according to blinded central reading. Secondary outcomes were the centrally read degree of endoscopic recurrence, perioperative data, postoperative morbidity, histopathological outcomes and use of Crohn's medication postoperatively.

**Discussion:** The SPICY trial will provide comprehensive evidence whether mesenteric sparing resection or extended mesenterectomy is better in terms of recurrence rates in ileocolic Crohn's disease patients undergoing an ICR. Details of the statistical analysis are described in this SAP.

**Registration number:** NCT00287612 (<http://www.clinicaltrials.gov>)

**Keywords:** Statistical analysis plan, Crohn's disease, ileocolic, extended mesenteric resection, recurrence

## INTRODUCTION

### Background and rationale

Crohn's disease is a chronic inflammatory bowel disease (IBD) affecting the entire intestinal tract. Up to 75% of patients require surgery during the course of the disease.[1] Unfortunately, surgery is not curative. Despite all initiatives to reduce postoperative recurrence rates, recurrence of the disease is rather a rule than an exception. Today, the optimal anastomosis [2-6] and the role of the mesentery [7-11] are widely discussed topics in the field of surgery for patients undergoing ICR, aiming to reduce postoperative recurrence. As early as 1932, dr. Crohn described the 'creeping fat' – fat envelopment of the mesentery around inflamed parts of the bowel – as one of the hallmarks of CD and opted for extended resection as treatment of the disease. [12] Currently, data on the anti- or pro-inflammatory role of the mesentery are conflicting. There is increasing evidence that the mesentery is actively involved in CD and reports suggest that excision of the affected mesentery could reduce postoperative recurrence rates.[8, 9] However, prospective data of a randomised controlled trial are lacking.

The SPICY trial was designed as a randomised controlled international superiority trial to demonstrate superiority of an extended mesenteric resection in terms of postoperative recurrence rates. The trial protocol was previously published.[13] The present SAP focuses on outcomes up to six months of follow-up and adheres to the JAMA Guidelines for the content of statistical analysis plans in clinical trials of which the checklist is demonstrated in the Supplementary materials.[14] This document has been written based on the study protocol version 10, dated 03-04-2022 (approved 21-04-2022).

## STUDY METHODS

### Objectives

The aim of the SPICY study was to determine whether extended mesenteric resection results in reduced postoperative recurrence rates in CD patients undergoing ICR, compared to a mesenteric-sparing ICR. The primary outcome is the endoscopic recurrence rate at six months postoperatively, defined as a modified Rutgeerts score of  $\geq 2b$ , according to central reading.

The secondary outcomes are:

1. The degree of postoperative endoscopic recurrence (classified according to the modified Rutgeerts score), according to blinded central reading by two experts.
2. Perioperative data (i.e. operative time, per-operative blood loss, conversion rate)
3. Postoperative outcomes
  - Postoperative morbidity <30 days (length of hospital stay, anastomotic leakage and Clavien dindo score.
  - Histopathological data (length of resected colon, length of resected ileum, inflammation resection margins)
  - Postoperative medication (continuation Crohns' medication postoperatively, endoscopically guided start of Crohns' medication)

### Framework

[figure not shown]
The SPICY trial was a superiority trial. The hypothesis for the primary analysis are as follows:

- Null hypothesis: There is no difference in the endoscopic recurrence rate between extended mesenteric resection and mesenteric sparing resection.
- Alternative hypothesis: There is a difference in the endoscopic recurrence rate between extended mesenteric resection and mesenteric sparing resection.

### Trial design

The SPICY trial was a two-arm international randomised controlled superiority trial. Patients undergoing ICR for ileocolic Crohn disease were randomised for either group 1 - conventional mesenteric sparing resection or for group 2 - extended mesenteric resection.

In mesenteric sparing resection, the mesentery was divided close to the bowel, as currently advised in the ECCO guidelines. [15] In the extended mesenteric resection, the mesentery was removed up to the origin of the ileocolic trunk. After identification of the ileocolic junction, the lower edge of the ileal branch of the ileocolic artery was followed distally, figure 1. The rest of the operation remained identical in both groups. A video vignette of the surgical procedure was published and shared with all participating centres as an example.[16]

**Figure 1. Surgical technique: a) Extended mesenteric resection following the lower edge of the ileocolic trunk; b) Mesenteric sparing ileocolic resection.**

Both groups followed standard postoperative care. Six centres participated in this trial in the Netherlands and Italy. The SPICY trial was registered under registration number NCT04538638 on August 31th 2020.

## **STUDY POPULATION**

### **Sample size**

This study was powered to detect a clinically relevant difference of 25 per cent in endoscopic recurrence at 6 months between the two techniques: 60 per cent versus 35 per cent (a risk reduction of 45 per cent). Assuming a chi-square test for two independent proportions powered at 80 percent and a two-sided  $\alpha$ -level of 0.05, a total of 62 patients in each surgical arm are required, for a total enrolment of 124 patients. Allowing for a 10 percent dropout, the aim was to enrol 138 patients.[13]

### **Screening for eligibility and recruitment**

Patients were screened for eligibility using the inclusion and exclusion criteria, as reported in the study protocol. [13] The number of eligible patients who did not want to participate will be reported and presented in the CONSORT flow diagram, figure 2.

### **Randomisation**

Eligible patients who consented were randomly assigned (1:1 ratio) to group 1 or group 2 by the research team, using CASTOR EDC randomisation software version 1.4. Randomisation was not stratified. In this study, patients, endoscopists and central readers were blinded to treatment allocation. Surgeons were not blinded.

## STATISTICAL PRINCIPLES

### **Analyses methods**

All statistical tests will be two-sided and results will be presented with 95% confidence intervals. P-values of less than 0.05 will be considered statistically significant. Missing data in baseline characteristics or outcomes will be reported.

#### *Baseline patient characteristics*

Baseline characteristics of the included patients will be reported by randomisation group and presented in table 1. Categorical variables will be summarised as numbers and percentages in each category. These data will be analysed using the chi-square or Fisher's exact test, depending on cell count. Continuous variables that are normally distributed will be summarised by mean and standard deviation; median and interquartile range in case of non-normal distribution. The distribution is checked using histograms and boxplots. Analysis of continuous variables will be performed using the Student's t-test and the Mann-Whitney U-test. Differences between study arms will be reported.

#### *Outcomes*

The primary endpoint, endoscopic recurrence rates, will be compared between two groups with Chi square testing (table 2). Secondary outcomes will be analysed using chi-Square or Fisher's exact test, as appropriate (table 3, 4). The degree of endoscopic recurrence, centrally read, will be presented in a bar chart, figure 3.

The latest available version (currently v.28) of the statistical program SPSS® (IBM, Armonk, New York, USA) will be used to perform analyses.

Additional analyses not mentioned in this analysis plan, but performed in response to journal reviewers will explicitly be qualified as post hoc.

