### **Timing of final analyses**

The SPICY trial was considered a low-risk trial by the Medical Ethical Committee of the Amsterdam UMC. Therefore, no data safety monitoring board was set up and no interim analysis was planned.

The statistical analysis of the primary (endoscopic recurrence) and secondary outcomes as previously described, will be performed and presented in the initial manuscript when every patient has reached six months follow-up, data entry and cleaning has been completed.

Figure 2. CONSORT FLOW diagram SPICY, intention to analysis for primary outcome parameter

Table 1 Baseline characteristics			
n (%) , median (IQR)	Extended mesenterectomy (n=)	Mesenteric sparing (n=)	p-value
Age at surgery, years			
Sex (male)			
Disease duration at surgery, months			
Smoker			
Active			
Ex-smoker			
BMI (kg/m  )			
Age at onset			
A1, ≤16 years			
A2, 16-40 years			
A3, ≥40 years			
Behaviour of disease			
B1, inflammatory			
B2, stricturing			
B3, penetrating			
Perianal disease			
Location of disease			
L1, terminal ileum			
L3, ileocolic			
Crohns' medication <12weeks before operation			
No medication			
Thiopurines			
Steroids			
Biologicals			
Small molecules			
BMI: body mass index			

Table 2. Primary outcome			
n %, median (IQR)	Extended mesenterectomy (n=)	Mesenteric sparing (n=)	P value
Endoscopic recurrence rate,			
Time between surgery and endoscopy, months			

Table 3. Secondary outcomes			
Outcomes central reading			
n (%)	Extended mesenterectomy (n=)	Mesenteric sparing (n=)	P value
Endoscopic recurrence rate, according to the modified Rutgeerts score			

*\*Degree of recurrence, according to tmodified Rutgeerts score will be presented in a bar chart, figure 3*

Table 4. Secondary outcomes			
Perioperative outcomes			
n %, median (IQR)	Extended mesenterectomy (n=)	Mesenteric sparing (n=)	P value
Per-operative data			
Operating time, hours			
Operative blood loss, cc			
Conversion rate			
Postoperative morbidity <30 days			
Length of hospital stay, days			
Anastomotic leakage			
Clavien Dindo score			
Histopathological data			
Radical resection			
Both sides no inflammation			
Distal inflammation			
Proximal inflammation			
Inflammation on both sides			
Length of resected ileum, cm			
Length of resected colon, cm			
Postoperative medication			
Continuation of Crohn medication immediately after surgery			

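### The rule for secondary outcomes names only categorical tests, although five of the secondary outcomes in Table 4 are continuous

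*SAP*

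**What the plan says.** The SAP section Outcomes gives one test rule for Tables 3 and 4: "Secondary outcomes will be analysed using chi-Square or Fisher's exact test, as appropriate (table 3, 4"). It names no other test for secondary outcomes.

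The section Objectives lists the secondary outcomes. They include "Perioperative data (i.e. operative time, per-operative blood loss, conversion rate") and "Histopathological data (length of resected colon, length of resected ileum, inflammation resection margins"), and length of hospital stay appears under postoperative morbidity. Table 4, printed under Timing of final analyses, gives these as measured quantities, for example "Operative blood loss, cc" and "Length of hospital stay, days". Operating time is in hours and the two resected lengths are in centimetres. The table header provides for medians with interquartile ranges, and there is a P value column. The SAP gives no cut-points that would turn these quantities into categories.

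Tests for continuous data appear in one other place, Baseline patient characteristics: "Analysis of continuous variables will be performed using the Student's t-test and the Mann-Whitney U-test". That paragraph opens with "Baseline characteristics of the included patients will be reported by randomisation group and presented in table 1", and the section Outcomes does not refer back to it.

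The section Analyses methods promises two-sided tests, 95% confidence intervals and a 0.05 threshold for all results.

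**The concern.** A chi-square or Fisher's exact test on a continuous variable treats each recorded value as an unordered category. It asks whether the two arms share the same set of values, not whether one arm tends to have larger ones. For operating time, blood loss, hospital stay and resected length, the second question is the one of interest.

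The analyst then has two options. One is to apply a test with little or no ability to detect a shift. The other is to depart from the stated rule and choose a test that the SAP does not assign to outcomes. Operating time, blood loss and hospital stay describe the operative burden of the more extensive resection, so their comparison should be fixed in advance. The rule also names no effect measure for these outcomes, so the promised confidence intervals have nothing to attach to.

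**Working it through.** **Inputs.** The SAP section Sample size gives "a total of 62 patients in each surgical arm are required, for a total enrolment of 124 patients", 60% versus 35% recurrence, 80% power, two-sided 0.05, and 138 patients after 10% dropout. The tests come from Outcomes and the five outcomes from Objectives and Table 4.

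**1. The plan's own sample size.** With mean proportion (0.60 + 0.35)/2 = 0.475:

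n per arm = [1.960 × √(2 × 0.475 × 0.525) + 0.842 × √(0.60 × 0.40 + 0.35 × 0.65)]² / 0.25² = (1.384 + 0.575)² / 0.0625 ≈ 61.4, rounded up to 62.

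Then 2 × 62 = 124, and 124/0.9 = 137.8, rounded up to 138. Power at 62 per arm is 80.4%. The stated figures are reproduced, and nothing below changes them.

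**2. Count of continuous secondary outcomes.** Operating time (hours), blood loss (cc), hospital stay (days), resected ileum (cm) and resected colon (cm): five. Time from surgery to endoscopy in Table 2 is also continuous, but it is not a listed secondary outcome and is not counted.

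**3. All values distinct, Pearson chi-square.** The table is 2 × 124 with one patient per column.
- Each expected count is 1 × 62/124 = 0.5.
- Each column contributes (1 − 0.5)²/0.5 + (0 − 0.5)²/0.5 = 1.
- Chi-square = 124 on (2 − 1)(124 − 1) = 123 degrees of freedom, p = 0.458.

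No term depends on which arm has the larger values. With unequal arms n₁ and n₂, each patient in arm 1 contributes n₂/n₁ and each in arm 2 contributes n₁/n₂, so the total is n₂ + n₁ = N again. With all 138 patients (69 per arm), chi-square is 138 on 137 degrees of freedom, p = 0.460.

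**4. All values distinct, Fisher's exact test.** The SAP's baseline section chooses between the two tests by cell count. With every expected count at 0.5, that choice leads to Fisher's exact test. Given the margins, each possible table has the same probability, 1/C(124, 62). The P value sums the probabilities of all tables no more likely than the one observed, which is all of them, so p = 1.

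**5. Contrast with a test that uses order.** Suppose every value in one arm exceeded every value in the other. Mann-Whitney U = 0, its null mean is 62 × 62/2 = 1,922 and its standard deviation is √(62 × 62 × 125/12) = 200.1, so |z| is about 9.6 and p is about 8 × 10⁻²². The results in steps 3 and 4 do not move. This is an artificial extreme that shows only how the tests behave.

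**6. Rounded values with ties.** The SAP gives no means or standard deviations, so the following are assumptions: operating time mean 140 min, SD 40; ileum 25 cm, SD 10; stay log-normal, median 5 days, log SD 0.5. A true shift of 0.5 SD (on the log scale for stay) was simulated with 62 per arm and 1,000 trials per setting. The share of trials with p < 0.05 was:

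| Outcome as recorded | Pearson chi-square | Mann-Whitney |
|---|---|---|
| Operating time, to the minute | 0% | 78% |
| Operating time, to 5 minutes | 6% | 78% |
| Ileum length, whole cm | 3% | 74% |
| Hospital stay, whole days | 20% | 77% |

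With no shift, chi-square rejected in 0.1% to 2.6% of trials, so it did not produce excess false positives here. Fisher's exact test was not simulated.

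**The case against.** The strongest reply is that the intent is plain. The sentence on the t-test and Mann-Whitney test refers to continuous variables in general, and both subsections sit under Analyses methods. A competent analyst would carry those tests over. The same paragraph separates normal from non-normal variables and says how this is judged, so the conventional pairing of test with distribution can be read from it. This stands as to intent, and the realistic consequence is therefore small. It does not repair the text. The baseline paragraph is tied to Table 1, while the outcome rule expressly covers Table 4 and names two other tests. Its closing qualifier can only choose between those two.

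A second reply concerns size. A reader might infer that none of the five outcomes can yield a meaningful P value, or that the plan would report p = 0.458. The SAP supports neither. Distinct values throughout are implausible for stay in days and unlikely for lengths if recorded in whole centimetres; with ties the P value is valid, only weak. And where all values are distinct, the choice by cell count gives Fisher's exact test with p = 1, so 0.458 belongs to the branch the plan would not take.

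A third reply is that requiring the Mann-Whitney test throughout would be reviewer preference. That also stands. The SAP's distribution-based rule is not shown to be wrong, and the header of Table 4 does not settle the matter, because Table 1 carries a similar header while the baseline text allows means and standard deviations.

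**Conclusion.** The stated rule is wrong for five secondary outcomes, which is more than missing detail, but the point is minor. Followed literally, the named tests ignore order. With all values distinct the result does not depend on the treatment effect, and this needs no assumption beyond distinctness and the planned numbers. With ties the loss is one of power. Its amount (0% to 20% rejection against 74% to 78%) rests on the assumed distributions, a 0.5 SD shift and the Pearson version of the test.

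The text is probably a drafting omission, and the SAP does not show that these unsuitable tests would in fact be run. Nor does the point reach the main result: chi-square suits the binary primary endpoint, and the sample size is reproduced as stated.

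**What to change.** Amend the SAP section Outcomes so that:

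- chi-square or Fisher's exact test applies to categorical secondary outcomes only;
- operating time, blood loss, length of hospital stay, and resected lengths of ileum and colon are compared by Student's t-test if normally distributed and by the Mann-Whitney U-test otherwise, with distribution judged as in the baseline section;
- each of these comparisons is reported with a between-group difference and 95% confidence interval, as Analyses methods promises.

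Naming the Mann-Whitney test for all five is an acceptable alternative. It fits the header of Table 4 and removes a choice made after seeing the data, but it is not required. If a Hodges-Lehmann estimate accompanies it, the text should say that this is the median of the pairwise between-arm differences, which need not equal the difference between the two medians shown. The same wording can cover time from surgery to endoscopy in Table 2 if a P value is given there.

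The cost is a sentence or two of SAP text and room in Table 4 for the difference and its interval. No new data are needed, and the primary analysis and sample size do not change.

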## Adherence and protocol deviations

### *Protocol deviation and violation*

Protocol deviations were predefined as follows:

- Not receiving the surgical treatment as assigned by randomisation, whether or not due to technical reasons.
- No endoscopy postoperatively.

Protocol violations are predefined as follows:

- Postoperative diagnosis other than Crohn's disease.
- Not receiving an anastomosis (in case of a (definitive-) stoma).

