### *Handling protocol deviations and violations, lost to follow up and withdrawal*

For each group the number of patients with protocol violation and deviation will be reported and specified with reasons. In case of withdrawal of consent and lost to follow-up, the number of patients will be reported, figure 2.

- In case of protocol violation, patient data will not be available for analyses and patients will be excluded from the trial.
- In case of protocol deviation patients will be included in the ITT analysis
  - o Not receiving the surgical treatment as assigned by randomisation, whether or not due to technical reasons → patients will be included in the ITT analysis according to the originally assigned study arm at baseline
  - o No endoscopy postoperatively → if a patient meets the 6 months follow up, but endoscopy could not be performed due to patients specific reasons (i.e. pregnancy), or the quality was insufficient to score endoscopic recurrence, MR or ultrasound to define recurrence will be accepted for the ITT analysis.
- In case of withdrawal of consent, patient data will not be available for analysis and patients will be excluded from the trial.
- Patients who are lost to follow up prior to the primary endpoint will be excluded from all outcome analyses. Baseline data will be reported.

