### **Analysis populations**

Data analyses will be conducted according to the intention-to-treat (ITT) principle. All included patients will be analysed according to their originally assigned study arm at baseline.

Two additional analyses will be considered:

- Per protocol analysis:

In the case of > 5% protocol deviations, a per-protocol analysis will be performed for patients who received endoscopy with a central reading score. All patients with a protocol deviation will be excluded from this analysis.

- As treated analysis:

[figure not shown]
In the case >5% patients not receiving their intervention as indicated by randomisation, an additional 'as treated' analysis will be presented with patients analysed in the study arm of the received treatment.

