### **Challenges**

The main challenge of the SPICY study was conducting the study and ensuring adequate follow-up during the COVID pandemic. In the published protocol, the primary endpoint was defined as endoscopic recurrence after six months. ECCO guidelines recommend surveillance endoscopy between 6 months and 1 year after surgery. Therefore, endoscopies performed later, due to longer waiting lists, were accepted (maximum median of 1 year per group is accepted).

Another challenge in designing the SPICY study concerned defining the eligible population. For this study, external validity was considered more important than internal validity because there are too many confounding factors during the perioperative phase (i.e. surgical procedure, anastomotic configuration and type of anastomosis, radicality of resection, presence of a perianal fistula and use of postoperative medication for other reasons). Therefore, a more heterogeneous group representative of the target population undergoing ICR surgery was included.

Finally, all patients in whom a recurrence was assessed around 6 months postoperatively were included in the ITT analysis. The aim of this study was to analyse whether extended mesenterectomy lowers the risk of developing postoperative recurrence (objectified by endoscopy, MR or ultrasonography). In the context of external validity, we present all results from patients with completed follow-up (ITT analysis). The percentages and degree of endoscopic recurrences, according to central reading, is presented separately.

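### Randomised patients left without an anastomosis are removed from every analysis, so the primary set is not intention-to-treat, and operative and 30-day outcomes that need no anastomosis are lost

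*SAP*

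**What the plan says.** Under Protocol deviation and violation, the SAP names two protocol violations. One of them is "Not receiving an anastomosis (in case of a (definitive-) stoma". The section on handling deviations and violations gives the consequence: "In case of protocol violation, patient data will not be available for analyses and patients will be excluded from the trial". What remains is a tally: "For each group the number of patients with protocol violation and deviation will be reported and specified with reasons".

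Analysis populations declares the intention-to-treat principle and adds: "All included patients will be analysed according to their originally assigned study arm at baseline". It names no modified ITT set, and no separate set for operative, 30-day or harms outcomes.

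The secondary outcomes under Objectives include "Perioperative data (i.e. operative time, per-operative blood loss, conversion rate"), then hospital stay, anastomotic leakage and Clavien-Dindo score within 30 days, then resected lengths and margin inflammation. Harms says that serious adverse events will be presented, and that every postoperative complication and re-intervention will be reported under postoperative morbidity. Randomisation says that surgeons were not blinded.

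**The concern.** Whether a patient receives an anastomosis is settled in the operating theatre, after allocation, by a surgeon who knows the arm. It may depend on how the operation went. Excluding on it breaks the comparison that randomisation protects, and the ITT label then tells readers that the protection is intact. If the included patients in Analysis populations are those left after the exclusions, the sentence is circular and the label is still wrong.

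The loss is plainest for the secondary outcomes. A patient who had the resection but no anastomosis still has an operating time, a blood loss, a hospital stay, a complication grade and a specimen. Of the listed 30-day outcomes, only anastomotic leakage needs an anastomosis. The SAP gives no reason for dropping the others, and a comparison of surgical morbidity that omits these patients could miss some of the more difficult operations. Counts with reasons would reveal an imbalance between arms, but not its effect on outcomes.

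**Working it through.** **The plan's own figures.** Sample size gives 60% v 35%, two-sided alpha 0.05 and power 80%. With the pooled-variance formula and mean rate 0.475,

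n per arm = [1.960 × √(2 × 0.475 × 0.525) + 0.842 × √(0.60 × 0.40 + 0.35 × 0.65)]² / 0.25² = 61.4, rounded up to 62.

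That is 124 in total, and 124 / 0.9 = 137.8, rounded up to 138. The stated figures reproduce, so the point does not concern the sample size.

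**Inputs for the illustration.** 138 patients give 69 per arm. The SAP gives no rate of patients without an anastomosis, so every count and risk below is an assumption. Five or seven such patients would be 5/138 = 3.6% or 7/138 = 5.1%, and would use 5 or 7 of the 138 − 124 = 14 places allowed for dropout.

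**Primary endpoint, no true effect.** Let the true recurrence rate be p = 0.45 in both arms, with k patients excluded from an arm and recurrence risk q among them. The rate in those kept is (69p − qk) / (69 − k), where 69p = 31.05.

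| Excluded, extended v sparing | q | Extended | Sparing | Spurious difference |
|---|---|---|---|---|
| 4 v 4 | any | equal | equal | 0 |
| 4 v 1 | 80% | 27.85/65 = 42.8% | 30.25/68 = 44.5% | −1.6 points |
| 4 v 1 | 45% | 45.0% | 45.0% | 0 |
| 4 v 1 | 20% | 30.25/65 = 46.5% | 30.85/68 = 45.4% | +1.2 points |
| 6 v 1 | 80% | 26.25/63 = 41.7% | 30.25/68 = 44.5% | −2.8 points |
| 6 v 1 | 20% | 29.85/63 = 47.4% | 30.85/68 = 45.4% | +2.0 points |

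Swapping the arms reverses the signs. The design difference is 25 points.

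**Effect on a test result** (chi-square without continuity correction; extended v sparing).

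- 4 v 4 excluded, 26/65 v 39/65 observed: p = 0.023. Counting all excluded as recurrence gives 30/69 v 43/69, p = 0.027. Counting none gives 26/69 v 39/69, p = 0.027.
- 4 v 1 excluded, 27/65 v 41/68 observed, a borderline case chosen for illustration: p = 0.031. All as recurrence gives 31/69 v 42/69, p = 0.061. None gives 27/69 v 41/69, p = 0.017.

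**Severe 30-day complications.** Assume a true 7/69 in both arms and 5 v 1 excluded.

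- None of the excluded had one: 7/64 − 7/68 = 10.9% − 10.3% = +0.6 points.
- Three of the 5 and the 1 had one: 4/64 − 6/68 = 6.3% − 8.8% = −2.6 points.
- All had one, the extreme case: 2/64 − 6/68 = 3.1% − 8.8% = −5.7 points.

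**The case against.** The rule is written down in advance, applies to both arms alike, and is disclosed with counts and reasons. Trial design says that the operation was otherwise identical in the two groups, so nothing shows that the number left without an anastomosis would differ by arm. One could also argue that endoscopic recurrence after ileocolic resection is naturally assessed at an anastomosis. On that view, the defect in the primary analysis is little more than a missing qualifier before ITT.

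Much of this stands for the primary endpoint: differential exclusion is possible but not shown, and the plausible shift is small. The assessability argument does not go far. The SAP does not make it, it already accepts MR or ultrasound when endoscopy is lacking, and it would justify at most a modified ITT set for recurrence. It gives no ground for dropping operative, 30-day or histopathology data.

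A reader might also infer further contradictions that the document does not support:

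- Patients who did not get the assigned operation are kept ("patients will be included in the ITT analysis according to the originally assigned study arm at baseline"), while these are removed. That is a deliberate split between deviations and violations. It is open to question but is not an inconsistency.
- Challenges says that "all patients in whom a recurrence was assessed around 6 months postoperatively were included in the ITT analysis". This is a recap in the discussion, and its context explains why imaging counts. It does not readily override an explicit exclusion rule.
- Challenges also says that "a more heterogeneous group representative of the target population undergoing ICR surgery was included". That sentence concerns who was eligible, not what happens after randomisation.

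Nor does the SAP say that harms in these patients go wholly unreported, since serious adverse events may still be presented.

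**Conclusion.** The point holds and should be fixed. The SAP conditions its main analysis set on an event after randomisation and calls the result ITT. Without a stated reason, it also removes operative, 30-day and histopathology outcomes that can be measured in these patients, against its own promise to report all complications. The second part carries most of the weight.

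The size cannot be known from the document. On assumed counts, the primary difference shifts by 0 when numbers and risks are balanced and by 1.2 to 2.8 points, in either direction, for 4 v 1 or 6 v 1 when the risk in those excluded is 20% or 80%. That would matter only for a borderline result. A reader might conclude that the primary comparison is seriously biased, but these figures do not support that. For severe morbidity the shift could be larger; −5.7 points needs every excluded patient to have had a severe complication.

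Two limits apply. Removing this rule would not by itself restore ITT, because the same section also excludes patients with a diagnosis other than Crohn's disease, those who withdraw consent and those lost to follow-up. And the bracketed qualifier on the stoma leaves unclear which stomas trigger exclusion, and so how many patients are affected.

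**What to change.** - Stop treating the absence of an anastomosis as grounds for exclusion from the trial.
- Analyse these patients by randomised arm in the perioperative, 30-day morbidity, histopathology and harms tables. Report anastomotic leakage among those with an anastomosis. If data collection stopped at exclusion, give the number with data per arm.
- For recurrence, use a 6-month assessment where one exists and otherwise treat the outcome as missing. Add two bounding sensitivity analyses, one counting all the missing as recurrence and one counting none.
- Call the primary set modified ITT as long as this exclusion, or those for diagnosis, withdrawal or loss to follow-up, remain.
- State which stomas the bracketed qualifier covers.
- Reconcile the sections on protocol violations, their handling, Analysis populations and Harms.

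The cost is SAP wording and one short sensitivity table, and the enrolment target stays at 138. The downsides are a few assumed outcomes in the sensitivity analyses and possibly incomplete data. The SAP says that violators' data will not be available, so if nothing was collected after exclusion, relabelling the set and reporting counts per arm may be all that can be done for those patients.
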